12.2.2.4 GI symptoms assessed by the investigator(s) at each time point

These variables will be analysed using the FAS only. In addition, these variables will be analysed using the FAS excluding the subjects who were judged not to have an ulcer scar by the central evaluation committee at baseline.

GI symptoms will be assessed for each subject at pre-dose and each time point of post-dose on the 4-point scale 'None', 'Mild', 'Moderate' and 'Severe'. For each of the six GI symptoms, a cross table of the severities at pre-dose and each time point of post-dose will be prepared. For subjects who have 'None' for a symptom at pre-dose, the percentage of the subjects who have the symptom at the subsequent time points will be calculated at each time point of postdose, and for subjects who have a symptom at pre-dose, the percentage of the subjects whose symptoms are resolved will be calculated at each time point of post-dose.

12.2.2.5 Safety variables

The safety evaluation of D20 will be performed based on AEs, clinical laboratory and vital signs (blood pressure and pulse rate) using the safety analysis set.

(a) AEs

AEs will be collected and recorded in the eCRF from the randomisation until the end of study. In addition, SAEs and DAEs will be collected and recorded from signing of informed consent. All AEs will be classified by system organ class and by preferred term using MedDRA. The number of subjects with AEs as well as total number of AEs will be summarised for each treatment group.

(b) Clinical laboratory test

Data of clinical laboratory values will be summarised for each treatment group using descriptive statistics.

(c) Vital sign

Data of vital signs (blood pressure and pulse rate) will be summarised for each treatment group using descriptive statistics.

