2.4 Safety objective

- Safety
 - To assess safety and tolerability of D20 versus placebo in patients with a history of gastric and/or duodenal ulcers on continuous LDA therapy by evaluating adverse events, clinical laboratory data, and vital signs (blood pressure and pulse rate).
- Long term safety
 - To assess long-term safety and tolerability of D20 during long-term treatment (52 weeks or longer) in patients (100 or more) with a history of gastric and/or duodenal ulcers on continuous LDA therapy by evaluating adverse events, clinical laboratory data, and vital signs (blood pressure and pulse rate).

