3.1 Overall study design and flow chart

This study is designed as a multinational, multicenter, randomized, double-blind, parallelgroup (2 groups), placebo controlled, Phase III study involving patients with a history of gastric and/or duodenal ulcers receiving daily LDA therapy. A total of 426 patients with a history of gastric and/or duodenal ulcers with ulcer scar confirmed by the esophagogastroduodenoscopy (EGD) performed at screening will be randomized 1:1 to either D20 group or placebo group. The efficacy and safety of D20 or placebo will be assessed after up to 72-week oral administration based on the results of the EGD performed at Weeks 12, 24, 36, 48, 60 and 72 after randomisation to verify presence or absence of gastric and/or duodenal ulcers, modified LANZA score to evaluate the degree of gastric and/or duodenal mucosal lesion and presence/absence and severity of RE evaluated by LA classification, and investigator's assessment for presence/absence and severity of gastrointestinal symptoms performed every 4 weeks. In addition, the safety of the concomitant use of D961H and LDA for a long-term period will be confirmed. If development of gastric and/or duodenal ulcer was observed in 36 patients, data will be cut off and analysed. Therefore, it is speculated to administer the test product for up to 72 weeks, but the period of administration of test product may not reach 72 weeks. (See Figure 1)

When development of gastric and/or duodenal ulcer was observed in at least 18 patients and at least 250 patients were randomized, the interim analysis will be performed by an independent data monitoring committee (IDMC) following the data cut-off, data cleaning and data base lock for the analysis. IDMC will decide on a recommendation on continuing or discontinuing the comparative analysis based on the results of the interim analysis (See Section 12.2.3). If IDMC recommend to continue the study, a final comparative analysis will be performed when development of gastric and/or duodenal ulcer is observed in at least 36 patients following the data cut-off, data cleaning and the database lock.

The sponsor will count the number of subjects in the D20 groups who have completed the tests at Visit 15 (Week 52) quickly after the completion of the comparative analysis (including the completion by the interim analysis).

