If the number is 100 or more, the sponsor will report the termination of the study to the investigator(s). The investigator(s) will perform the tests required for Visit 20 to all subjects at the next visit after receiving the report and will make the subjects complete the study.

If the number is less than 100, the sponsor will report the continuation of the study and the key information of each subject at the site to the investigator(s). The investigator(s) will perform the tests required at Visit 20 to subjects who are randomised to placebo at the next visit after receiving the report and will make the subjects complete the study. For subjects who are randomised to D20, if the next visit after receiving the report is Visit 15 (Week 52) or later, the investigator(s) will perform the tests required for Visit 20 to the corresponding subjects at the visit and will make the subjects complete the study. If the next visit after receiving the report is before Visit 15 (Week 52), the investigator(s) will perform the tests required at the visit and make the subjects continue the study until Visit 15 (Week 52) after confirming that the subjects want to continue the investigational treatment. If subjects do not want to continue

the investigational treatment, then the investigator(s) will perform the tests required for Visit 20 and will make the subjects complete the study at the visit. The sponsor will report the termination of the study to the investigator(s) as soon as the number of subjects in the D20 group who have completed Visit 15 is reached 100 or more. The investigator(s) will perform the tests required for Visit 20 to all subjects at the next visit after receiving the report and will make the subjects complete the study.

EGD findings judged as an evidence of an ulcer scar at screening, those previously confirmed as ulcers and those judged as gastric and/or duodenal ulcers by the investigator(s) after randomisation as gastric and/or duodenal ulcers will be reviewed by the central evaluation committee (see Section 12.4) established by the sponsor under the blinded conditions any time.

Figure 2 shows the study design and Table 2 shows the study plan including frequency and time of visits.

*1 Investigators notice the study completion to the subjects, if applicable, at the next visit after the key broken. (See Section 5.8.2)

Table 2Study plan

Period	Screenin	aing Study treatment																		
		Rand omiz ation																		

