6.4.3 Recording of adverse events

Time period for collection of adverse events

Adverse Events will be collected from the randomization date (Visit 2) to the last scheduled visit or withdrawal.

SAEs will be recorded from the time of informed consent.

Follow-up of unresolved adverse events

Any AEs that are unresolved at the subject's last AE assessment or other assessment/visit as appropriate in the study are followed up by the investigator for as long as medically indicated, but without further recording in the eCRF. AstraZeneca retains the right to request additional information for any subject with ongoing AE(s)/SAE(s) at the end of the study, if judged necessary.

Variables

The following variables will be collect for each AE;

• AE (verbatim)

- Date when the AE started and stopped
- Maximum intensity
- Whether the AE is serious or not
- Investigator causality rating against the Investigational Product (yes or no)
- Action taken with regard to investigational product
- AE caused subject's withdrawal from study (yes or no)
- Outcome
- Investigator causality rating against the mucosal protectant (yes or no)

In addition, the following variables will be collected for SAEs:

- Date AE met criteria for serious AE
- Date Investigator became aware of serious AE
- AE is serious due to
- Date of hospitalisation (if applicable)
- Date of discharge (if applicable)
- Date of death (if applicable)
- Probable cause of death (if applicable)
- Autopsy performed
- Causality assessment in relation to Study procedure(s)
- Causality assessment in relation to Other medication
- Causality assessment in relation to mucosal protectant provided by AstraZeneca
- Description of AE.

It is important to distinguish between serious and severe AEs. Severity is a measure of intensity whereas seriousness is defined by the criteria in Section 6.4.2. An AE of severe intensity need not necessarily be considered serious. For example, nausea that persists for several hours may be considered severe nausea, but not a SAE unless it is fulfilled with the

definitions in Section 6.4.2. On the other hand, a stroke that results in only a limited degree of disability may be considered a mild stroke but would be a SAE.

Maximum intensity of the reported AEs will be assessed according to the following scale:

- Mild (Awareness of sign or symptom, but easily tolerated)
- Moderate (Discomfort sufficient to cause interference with normal activities)

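### If fewer than 100 D20 subjects have completed Week 52 at key break, crude adverse event counts to end of study set longer, partly unblinded D20 follow-up against shorter placebo follow-up

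*Protocol*

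**What the plan says.** Section 2.4 sets a comparative safety objective, "To assess safety and tolerability of D20 versus placebo in patients with a history of gastric and/or duodenal ulcers on continuous LDA therapy", and a separate long-term objective for D20 (52 weeks or longer, 100 or more patients). Section 12.2.2.5 has one AE summary for both. On collection it says "AEs will be collected and recorded in the eCRF from the randomisation until the end of study". On analysis it says "The number of subjects with AEs as well as total number of AEs will be summarised for each treatment group". It names no time denominator and no cut at key break. Section 9.5 defines the end of study as the last visit of the last subject. Section 6.4.3 gives the window for each subject: "Adverse Events will be collected from the randomization date (Visit 2) to the last scheduled visit or withdrawal". The safety set in section 12.1.2 is not limited to the blinded period.

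Section 3.1 sets what happens after the comparative analysis, including one that ends at the interim: "The sponsor will count the number of subjects in the D20 groups who have completed the tests at Visit 15 (Week 52) quickly". With 100 or more, everyone finishes at the next visit. Otherwise, "If the number is less than 100, the sponsor will report the continuation of the study and the key information of each subject". Placebo subjects then finish at the next visit. For D20 subjects who have not reached Week 52 and who agree, the investigators "make the subjects continue the study until Visit 15 (Week 52"). This extension closes once 100 D20 subjects have completed that visit. Section 5.8.2 repeats the rule.

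**The concern.** A count of subjects with at least one AE, or of AEs, grows with time under observation. On the under-100 branch one arm is observed for longer than the other, and the extra time is spent with the treatment known to the site. If the counts for the comparative objective include that time, D20 can show more AEs than placebo when the true rates are the same. The artefact goes against the sponsor's own drug, and it touches one of the trial's two safety objectives. Knowledge of the code may also change what is reported; that effect is not quantified here.

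**Working it through.** **Inputs from the protocol.** Section 12.3: 6-month ulcer rates of 1.5% (D20) and 7.4% (placebo), 213 per arm, 12 months of recruitment, 18 months in total, 15% discontinuing without an event, 36 events. Section 12.2.3: interim at 18 events, with at least 250 randomised. Section 5.8: an ulcer ends treatment. Section 3.1: the branch rule, using its count of D20 completers. (Section 5.8.2 words that count without limiting it to D20; the two should be reconciled.)

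**Assumptions not in the protocol.** Uniform entry, constant hazards, all eligible D20 subjects agree to continue, the timing of dropout, the lag from data cut-off to key break, and the AE rate.

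**1. Timeline.** Monthly hazards are −ln(1−0.074)/6 = 0.0128 on placebo and −ln(1−0.015)/6 = 0.0025 on D20. Without dropout, expected events per arm by month T ≥ 12 are (213/12)∫₀¹² [1−exp(−λ·min(T−a, 72 weeks))] da.
- Month 18 gives 36.3 events, which reproduces the plan's 36. With 15% dropout per year it is 33.4, and 36 events arrive between months 19 (35.5) and 20 (37.3).
- Month 12 gives 18.8 events (17.8 with that dropout), so the interim falls near month 12.
- 250 subjects are in by month 12×250/426 = 7.0, so that condition causes no delay.

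**2. How likely is an interim stop?** At half the information the Pocock-like spending function gives 0.05·ln(1+(e−1)·0.5) = 0.0310, or z = 2.157. (The protocol's 2.94% gives z = 2.178, which makes no practical difference.) In 1,500 simulated trials, with 15% dropout over 18 months, the log-rank test at the interim crosses in about 82%. With the 1.1% that Table 1 shows for D20 it crosses in about 93%. Over 97% of the interim stops fall on the under-100 branch.

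**3. Person-years by month of key break.** These come from numerical integration over entry. Placebo stops about two weeks after key break. D20 goes on to Week 52 or until 100 completers. Ranges cover dropout of 0% to 15% per year.

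| Key break | D20 completers of Week 52 | Placebo person-years | D20 person-years | Ratio | Ratio if both arms are cut |
|---|---|---|---|---|---|
| Month 12 | 0–1 | 103–109 | 179–186 | 1.71–1.74 | 1.04 |
| Month 14 | 30–35 | 132–141 | 183–190 | 1.35–1.38 | 1.05 |
| Month 16 | 59–70 | 160–173 | 191–200 | 1.16–1.19 | 1.06 |
| Month 18 | 88–104 | 185–201 | 202–215 | 1.07–1.09 | 1.07 |

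The last column is what remains because more placebo subjects leave with an ulcer.

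**4. Exposure after a simulated interim stop.** The ratio is 1.71 with no lag, 1.47 with 1.5 months (mean exposure about 10.5 months on D20 and 7.1 on placebo) and 1.29 with 3 months. Cutting both arms at the first visit after key break brings it to about 1.05.

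**5. Effect on crude AE incidence.** Take the same first-AE rate r per year in both arms and average 1−exp(−r × exposure in years) over subjects, with the 1.5-month lag.
- r = 1: about 57% on D20 and 42% on placebo (ratio 57/42 = 1.36).
- r = 0.5: about 35% and 25% (ratio 35/25 = 1.40).

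As a rough check from the mean exposures at r = 1, 1−exp(−10.5/12) = 58% and 1−exp(−7.1/12) = 45%. Averaging over unequal individual exposures lowers both. Rates per patient-year are equal here by construction.

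**The case against.** The strongest reply is that the protocol does not say the extension data enter the comparative table. The words about the end of study belong to the sentence on collection, and the summary sentence gives no window. Section 3.1 puts a cut-off and database lock before the comparative analysis, and the long-term objective stands apart. Data windows and person-time rates are usual content for a statistical analysis plan, which section 12.2 promises. This stands in part: the absence of exposure-adjusted rates would not by itself be a finding. But the protocol is not silent. It states the collection window and the statistic, it ties no AE table to the cut-off, and its own stopping rule makes that statistic non-comparable.

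Four further limits stand in full.
- The problem is conditional. With 100 or more completers both arms stop together.
- Crossing the boundary is not the same as stopping. The monitoring committee only recommends.
- Continuation needs the subject's agreement and closes at 100 completers, so the ratios for the extension are upper figures on that score.
- The AE summary is descriptive, with no test. AE start and stop dates are recorded (section 6.4.3), so events before and after key break can be separated.

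A reader might infer that the safety comparison is biased by design whatever happens, that a real difference could never be told from exposure, or that laboratory and vital-sign tables share the fault. The documents support none of these. The first ignores the condition, the second ignores the dated events, and nothing calculated here shows bias in descriptive laboratory or vital-sign summaries.

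**Conclusion.** The point holds conditionally. If key break finds fewer than 100 D20 subjects at Week 52, AE counts to end of study mix blinded parallel follow-up with unblinded D20-only follow-up, and they answer the D20-versus-placebo objective misleadingly. Under the plan's own rates this branch is the likely one after an interim stop, with an exposure ratio of about 1.3 to 1.7. If the trial runs to 36 events near month 18 the ratio is about 1.07 to 1.09, nearly all of it from ulcer withdrawals, and the extension adds little or nothing. The direction follows from the text. The size rests on the assumptions listed in the working, above all the key-break lag, full agreement to continue and the AE rate. It should be corrected because the remedy is cheap and needs no change in conduct or data collection.

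**What to change.** In section 12.2.2.5(a):
- Base the D20-versus-placebo AE summary on data up to each subject's first visit after key break, in both arms.
- Add AE rates per 100 patient-years beside the counts. These also handle the residual ratio of about 1.05 from ulcer withdrawals, provided the AE rate is roughly constant over time.
- Report D20 data after that visit in a separate table, labelled uncontrolled and unblinded, for the 52-week objective.

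The cost is protocol wording and one extra set of tables. The downside is that late D20 events appear in the second table, so the long-term report must show both. On the under-100 branch the cut still leaves a short interval, up to the next 4-weekly visit, in which sites may know the code; it applies to both arms alike.

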12.2.3 Interim analyses

A single interim analysis to assess the superiority of D20 to placebo in the time to occurrence of peptic ulcer from randomisation will be performed when a minimum of 18 events have occurred in the overall population. However, if the number of randomised subjects is less than 250 at the time 18 events are confirmed, then the interim analysis will be postponed until 250 subjects are randomised.

After 18 events are observed, a date of the data cut off for the interim analysis will be decided as soon as possible. An event observed after the data cut off will not be used for the interim analysis.

The adjustment of the multiplicity for statistical tests will done using the Pocock-like alphaspending function with Lan-DeMets approach, resulting that the nominal significance level will be two-sided 2.94% (Pocock SJ 1977) if exactly 18 events overall are reported at the time of the interim analysis. The exact nominal significance level will be determined based on the exact number of events at the time of the interim analysis.

The blind must be kept until the database lock for the interim analysis and after the database lock, the statistician of the IDMC will perform the interim analysis and will present the results to the other members of the IDMC. The IDMC will then make a recommendation that the study be stopped, amended or continue unchanged.

If 36 patients had an occurrence of gastric and/or duodenal ulcer prior to the randomisation of 250 patients, then the interim analysis will be cancelled.

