12.2 Methods of statistical analyses

A comprehensive Statistical Analysis Plan (SAP) will be prepared before unblinding of the data. A significant level of p<0.05 (two-tailed) will be used, in principle, for statistical tests and interval estimation.

All statistical analyses in this study will be performed by Statistics and Programming Department of AstraZeneca K.K. using the SAS software.

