12.3 Determination of sample size

The sample size for this study was selected to be consistent with the research hypothesis as described in Section 1.2.

The primary variable of this study is the time from randomisation to occurrence of peptic ulcer. The result of a phase III study (D961FC00003) was used to estimate the occurrence rates of peptic ulcer at 6 months for D20 and placebo. The event rates for peptic ulcer at 6 months were 1.5% for D20 and 7.4% for placebo, respectively.

In order to detect a difference in time to occurrence of peptic ulcer between D20 and placebo with two-sided 2.94% significance level and >90% power, assuming a recruitment period of 12 months and a minimum follow-up of 6 months; i.e. the total length of study is estimated to be 18 months, at least 36 events will be required. To get the number of events during the period in total 426 subjects (213 subjects per group) will be randomised in the study taking 15% of subjects who may discontinue the study without an event into consideration.

The final analysis of the primary variable will be performed when 36 events are observed. The nominal 2-sided significance level for all analyses will be 5%, except for the primary variable, where the nominal significance level will be adjusted using the Pocock-like alphaspending function with Lan-DeMets approach to allow for a single interim analysis.

In this study, at least 100 subjects who are randomised to D20 will continue taking investigational product for one year to obtain long-term safety data because one-year safety data from at least 100 subjects are required according to the ICH E1 guideline "The Extent of Population Exposure to Assess Clinical Safety for Drugs Intended for Long-Term Treatment of Non-Life-Threatening Conditions".

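### The 2.94% interim level in section 12.2.3 is the classical two-look Pocock constant; the Lan-DeMets Pocock-like function that the plan names gives 3.10% at 18 of 36 events, with 2.77% at the final analysis

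*Protocol*

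**What the plan says.** The overall level is set in Protocol section 12.2: "A significant level of p<0.05 (two-tailed) will be used, in principle, for statistical tests and interval estimation". Section 12.2.3 plans one interim look ("A single interim analysis to assess the superiority of D20 to placebo"), which "will be performed when a minimum of 18 events have occurred in the overall population". It is postponed if fewer than 250 subjects have been randomised by then.

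The adjustment is made "using the Pocock-like alphaspending function with Lan-DeMets approach". The numerical consequence is given in the same sentence: "resulting that the nominal significance level will be two-sided 2.94" percent, on the condition that the interim falls at exactly 18 events. The next sentence of section 12.2.3 says that the exact level will follow from the actual number of events at the interim.

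Section 12.3 fixes the end point of the information scale: "The final analysis of the primary variable will be performed when 36 events are observed". It computes the required events "with two-sided 2.94% significance level and >90% power". It also says that the primary variable is tested at a nominal level adjusted by the same spending function. No figure is printed as the final threshold.

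**The concern.** Section 12.2.3 presents 2.94% as the output of the spending function, but cites beside it the 1977 paper on fixed group sequential boundaries. These are two different rules. The fixed Pocock boundary uses one constant at equally spaced looks. The Lan-DeMets Pocock-like function approximates it and allows any spacing, but its levels at the two looks are not equal and neither is 2.94%.

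The figure is the stopping threshold of the only confirmatory test. At exactly 18 events, an interim p-value of 0.030 is significant under the named function and not significant under the printed number, so two answers can be drawn from one sentence. Because 2.94% appears again in section 12.3 and no final level is printed, someone looking for a number for the final test finds only 2.94%, which is above what the function allows.

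**Working it through.** **Inputs.** Two-sided α = 0.05 (section 12.2); one interim and one final analysis (12.2.3); 18 interim events (12.2.3) and 36 final events (12.3), so the information fraction is t = 18/36 = 0.5. The protocol does not print the spending formula. I take the standard Pocock-like form, α(t) = α·ln(1+(e−1)t). The two log-rank statistics are treated as bivariate normal with correlation √t, and the overall error is 1 − P(|Z₁| < c₁, |Z₂| < c₂).

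**Step 1: reproduce the printed figure.** Solve for one constant c at both looks with correlation √0.5 and overall error 0.05. This gives c = 2.178, two-sided p = 0.02939, that is 2.94%. The printed number is the fixed Pocock boundary for two equally spaced looks.

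**Step 2: apply the named function.**
- Interim: 0.05·ln(1 + 1.71828·0.5) = 0.05·ln(1.85914) = 0.03101, so 3.10%, z = 2.157.
- Final: solve for c₂ with c₁ = 2.157 and total error 0.05. This gives c₂ = 2.201, p = 0.02774, so 2.77%.

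Other conventions do not rescue 2.94%. Spending 0.025 one-sided and doubling gives the same 3.10%. The O'Brien-Fleming-type function gives 0.56%. The Pocock-like function equals 2.94% only at t = 0.466, or 0.466·36 ≈ 16.8 events, which is below the minimum of 18.

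**Step 3: overall two-sided error of each pair of thresholds at 18/36 events.**

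| Interim | Final | Overall error |
|---|---|---|
| 2.94% | 2.94% | 5.00% |
| 3.10% | 2.77% | 5.00% |
| 2.94% | 2.77% | 4.87% |
| 3.10% | 2.94% | 5.13% |

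**Step 4: a later interim.** The wait for 250 randomised subjects makes a count above 18 possible.

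| Interim events | Function, interim | Function, final | Error: function interim, 2.94% final | Error: 2.94% at both |
|---|---|---|---|---|
| 20 | 3.35% | 2.65% | 5.22% | 4.89% |
| 24 | 3.82% | 2.47% | 5.32% | 4.64% |
| 27 | 4.14% | 2.39% | 5.32% | 4.41% |
| 30 | 4.44% | 2.39% | 5.27% | 4.15% |
| 34 | 4.82% | 2.71% | 5.06% | 3.64% |

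**Step 5: does the sizing survive?** Section 12.3 gives 6-month event rates of 1.5% and 7.4%. Under exponential times the hazard ratio is ln(0.985)/ln(0.926) = 0.197.
- Schoenfeld, power = Φ((√36/2)·|ln HR| − z): Φ(4.880 − 2.178) = 99.7% at 2.94% and Φ(4.880 − 2.201) = 99.6% at 2.77%.
- Freedman, power = Φ(√36·(1−HR)/(1+HR) − z): Φ(4.029 − 2.178) = 96.8% at 2.94% and Φ(4.029 − 2.201) = 96.6% at 2.77%.

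The event requirement and the power statement are unaffected.

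**The case against.** The strongest reply is that the printed figure does no harm. At exactly 18 events 2.94% is stricter than 3.10%, so following it literally at the interim cannot raise the type I error. It is also conditional: it applies only at exactly 18 events, and for any other count section 12.2.3 already has the level recomputed. The gap where both readings compete is 3.10 − 2.94 = 0.16 percentage points. All of this stands and keeps the point minor. It does not make the figure correct.

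Two stronger readings are tempting. A reader might infer that section 12.3 fixes the final test at 2.94%. It does not: there 2.94% is the significance level used to compute the events, and the same section sends the primary test to the spending function. A reader might also infer that combining the two rules overspends alpha and that 5% control is broken. Of the four pairs at 18/36 events, only a 3.10% interim followed by a 2.94% final exceeds 5%. Reaching that pair means setting aside 2.94% where it is printed as a threshold and then using it where the text calls for the spending function. The documents do not prescribe this. The possibility remains open only because the final level is never given as a number.

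**Conclusion.** The point holds as a wrong stated threshold with a small effect. The method named in section 12.2.3 gives 3.10% at the interim and 2.77% at the final analysis for 18 and 36 events; 2.94% belongs to a different rule. The printed interim figure is slightly conservative. Inflation, of 0.13 percentage points at 18 events and about 0.3 at most with a later interim, depends on a pairing that the protocol does not prescribe. The design quantities do not move.

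The result assumes the standard Pocock-like spending formula, information measured by event counts, and the usual joint normality of the two log-rank statistics. With so few events the normal approximation is itself rough, but that does not change which rule produces which number. Severity: minor.

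**What to change.** In section 12.2.3, replace 2.94% with 3.10% at the interim and 2.77% at the final analysis, for exactly 18 and 36 events. Give the formula α(t) = 0.05·ln(1+(e−1)t), and say that the levels at both looks are recomputed from it at the actual event counts, the final one taking account of the alpha spent at the interim. In section 12.3, use 2.77% as the sizing level. This should be settled before any unblinded interim result exists, because a later choice between two thresholds could look data-driven.

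Naming the fixed Pocock boundary would make 2.94% correct at 18/36 events, but it fits this plan less well. The interim count can exceed 18, and holding 2.94% at both looks would then waste alpha (4.89% overall at 20 events, 4.15% at 30).

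The cost is a few words in two sections and a slightly stricter sizing and final level. Power falls by about 0.1 to 0.2 percentage points, and the 36 events and 426 subjects stay as they are.
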